The objective of this study is to assess the efficacy of a SHPB for pain relief following laparoscopic hysterectomy. The superior hypogastric plexus lies in the presacral space and supplies autonomic innervation to the central pelvis. This plexus is suspected to play a role in postoperative pain following a hysterectomy. We hypothesize that a SHPB using the anesthetic bupivacaine will reduce patients' pain scores and opioid consumption following a laparoscopic hysterectomy.

VIII. Trial design:

This study is designed as a multi-center, randomized, single-blind, controlled trial of patients scheduled for a laparoscopic hysterectomy. Patients will be randomized to two groups: one group will receive a SHPB and laparoscopic hysterectomy, and the other will receive no block and laparoscopic hysterectomy.

METHODS

IX. Study setting:

The study will be conducted at three sites: Brigham and Women's Hospital (BWH)/Brigham and Women's Faulkner Hospital(FH), University of North Carolina Medical Center (UNC) and George Washington University (GWU).

X. Eligibility criteria:

Patients over 18 years of age who are scheduled for a laparoscopic hysterectomy at participating sites will be recruited to participate. Patients of all comorbidities will be eligible for inclusion; specifically, patients with chronic pain syndromes will not be excluded so as to evaluate the efficacy of SHPB in this population. The exclusion criteria include patients who are unwilling to consent, who have an allergy to block medications used in the trial, are undergoing a sacrocervicopexy or a sacrocolpopexy, are undergoing a laparotomy, or those with anatomy that limits the safe application of a presacral injection (per the surgeon's discretion at the time of the procedure). Patients will not be excluded if they undergo other concomitant procedures during laparoscopic hysterectomy. While concomitant procedures may contribute to patients' pain following laparoscopic hysterectomy, this will improve the external validity of the trial. Moreover, randomization should balance differences in patients and procedures between the two treatment arms.

XI. Interventions:

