and the incisional block will contain 50 mg of bupivacaine (20 mL of 0.25% bupivacaine, 2.5 mg/mL) for a total dose of 75 mg. The maximum safe dose of bupivacaine is 2 mg/kg therefore all patients with a weight over 37.5 kg (82.5 lbs) will be safe to receive this dose. This weight threshold encompasses nearly all women over age 18. In the very unlikely event that a patient weighs less than this, the incisional block will be reduced accordingly. No additional bupivacaine will be used during the procedure. Patients with an allergy to bupivacaine will be excluded from the study.

Patients will be charged for the bupivacaine anesthetic as it is a standard component of a laparoscopic hysterectomy and is routinely injected in the incisions for local anesthesia. All patients will be receiving the anesthetic in the incisions regardless of the treatment arm. Only patients in the SHPB arm will also receive the anesthetic in the presacral space. This is not anticipated to add cost to the procedure as all patient in the study will receive this medication.

XII. Outcomes:

The primary outcome will be immediate postoperative patient pain scores (within 4 hours) using the Visual Analog Scale (VAS) in the recovery unit. The secondary outcomes will be intraoperative and postoperative opioid consumption as well as VAS pain scores from the Brief Pain Inventory (BPI) as recorded in a patient diary for one week following surgery. Subgroup analyses will be performed on patients undergoing a hysterectomy for pelvic pain and patients who undergo a laparoscopic hysterectomy without concomitant procedures.

XIII. Participant timeline:

Participation starts with enrollment and an eligibility screen. Eligible patients who agree to participate will be consented on the day of surgery. Patients will undergo surgery and be followed up to eight weeks postoperatively.

XIV. Sample size:

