A sample size was determined using prior data on the increased percentage of patients with low VAS scores following SHPB and abdominal hysterectomy.¹⁰ Sixty-three percent of women in the ropivacaine group had a VAS pain score less than 4 at two hours postoperatively, compared to 25% in the placebo group ($p=0.015$). A two-sample comparison of proportions with a beta error of 0.2, alpha error of 0.05, and 10% loss to follow-up, therefore requires a sample size of 58 patients. Accounting for heterogeneity in the patient population we aim to recruit 100 patients, with 50 in each treatment arm. Patients will be enrolled at BWH, FH, UNC and GWU, with approximately 50 patients coming from BWH/FH, 30 patients from UNC and 20 patients from GWU. We expect to enroll approximately 20 patients per month between the three sites. Data collection is anticipated to take approximately seven months, accounting for postoperative evaluation up to eight weeks after surgery.

XV. Recruitment:

Recruitment begins at the initial consult visit. The surgeon will explain the study, and then ask the patient if they would like to hear more about it. Only patients that affirm that they are

interested will then be given a description of the study protocol and a copy of the consent form to take home with them (Appendix “SHPB Consent Form”). If a subject decides they do not want to participate, a decline card will be included in the materials. A research assistant will also contact subjects by phone to answer any questions regarding the study. Patients who remain interested in participating will be formally consented on the day of surgery by one of the participating surgeons.

XVI. Assignment of interventions, allocation concealment, and implementation:

Patients will be randomized on the day of surgery after informed consent has been obtained. Subjects will be randomized using urn randomization with a 1:1 allocation of treatment and placebo, stratified by the three sites (BWH/FH, UNC and GWU). Randomized allocation of the treatment arms will be concealed in sequentially-numbered, opaque, sealed envelopes. The randomization sequence and concealed allocation envelopes will be prepared by a research assistant and unknown to the remainder of the study staff.

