Patients will be randomized to two treatment groups: one group will receive the SHPB, and the other will receive no block. Patients will be randomized after informed consent is confirmed on the day of surgery. Subjects will be randomized using urn randomization with a 1:1 allocation of treatment and placebo, stratified by the three sites (BWH/FH, UNC and GWU). Randomized allocation of the treatment arms will be concealed in sequentially-numbered, opaque, sealed envelopes. The randomization sequence and concealed allocation envelopes will be prepared by a research assistant and unknown to the remainder of the study staff. A placebo arm (e.g. presacral injection of saline) was not designated given little to no anticipated benefit of a sham block. For the treatment arm, the risks of presacral injection are anticipated to be very rare and superseded by the potential benefit of reduced postoperative pain as demonstrated in patients undergoing abdominal hysterectomy.¹⁰

XVII. Blinding:

Patients will be blinded to the treatment arm; however, the surgeon and operating room staff will know if a patient has been randomized to receive the block during the hysterectomy. Nurses in the recovery unit and on the inpatient floors will also be blinded to the treatment arm. The Medication Administration Record will document a blinded medication for patients in the trial to reduce the risk that staff caring for patients outside the operating room become aware of the treatment arms.

XVIII. Data collection methods:

Postoperative pain scores will be collected by a registered nurse upon admission to the recovery unit, and at every hour for four hours or until the patient is discharged. Most patients are discharged home on the same day as surgery with a recovery unit stay between two to six hours depending on the patient. If a patient is admitted to the hospital, the worksheet will be completed by the recovery unit nurse for as long as the patient is in the recovery unit and completed by the floor nurse for a total of four hours postoperatively. Pain scores will be

collected using the Visual Analog Scale to ask patients their pain level on a scale of 0 to 10, where 0 indicates no pain and 10 indicates the worst pain imaginable.

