Intraoperative and immediate postoperative opioid consumption will be collected from the Medication Administration Record. The nursing staff will also be asked to complete a recovery worksheet that details the VAS pain score and opioid administration on admission to the recovery unit and every postoperative hour until four hours or the patient is discharged (Appendix “SHPB RN Worksheet”). The nursing staff will also be asked to note the total time the patient was in the recovery unit. Patients will also be asked to complete a daily diary for one week following the procedure, which details their pain level and daily opioid consumption (Appendix “SHPB Patient Diary”).

Patients will be followed for eight weeks after surgery to assess for the occurrence of any postoperative complications. Detailed patient and procedure characteristics including age, race, body mass index, parity, surgical history, surgery indication, procedure type, and surgical approach will also be collected.

No additional follow-up visits will be required; however, the patient will be asked to return their postoperative diary at their routine postoperative visit (approximately four weeks after surgery). To avoid loss to follow-up, patients will be contacted one to three days after surgery or discharge to remind them to complete the daily diary for one week postoperatively. Patients who have a prolonged hospital stay or who are readmitted to the hospital during the first postoperative week will be reminded to complete the diary as an inpatient, and their narcotic consumption obtained from the medical record. Patients who do not schedule a routine postoperative visit or who forget to bring the diary to their postoperative visit will be contacted by phone or mail and a stamped and addressed envelope sent to their home address for them to return the diary.

XIX. Data management:

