All healthcare personnel involved in this study will be responsible for completing correct operative and postoperative data. Patients will be asked to complete a daily postoperative diary which they will return at their postoperative visit. All other data points will be abstracted from patient medical records by research assistants. A minimum number of persons will be involved with the data abstraction in an attempt to decrease introduction of bias. The research assistants will also keep a copy of all source documents such as informed consent on file. All data will be kept in password-protected computer systems, locked file cabinets, and offices accessible only to study staff.

XX. Statistical methods:

Statistical analysis will be performed to test the null hypothesis that there is no difference in VAS pain scores or opioid consumption following laparoscopic hysterectomy with and without a SHPB. The primary analysis will be intention to treat, i.e. those patients randomized to the two treatment arms regardless of the intervention or outcome assessment. The primary outcome (immediate postoperative VAS pain scores in the recovery unit for four hours) will

be treated as continuous as well as dichotomized variables and compared using Student's t-tests if continuous and normally distributed, Wilcoxon tests if continuous and non-normally distributed, and Chi-square tests if dichotomized. A linear regression will be performed to adjust for the two participating sites. As patients are randomized to the two treatment groups, no additional adjustment for potential confounding variables is anticipated to be necessary. Subgroup analyses will be performed on patients undergoing a hysterectomy for pelvic pain and patients who undergo a laparoscopic hysterectomy without concomitant procedures. The final analysis will be conducted at the 0.05 level of significance and the interim analysis will be conducted at the 0.002 level of significance (to minimize type I error). Statistical analysis will be performed using appropriate statistical software and with the assistance of a biostatistician.

XXI. Data monitoring:

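### No section describes a preoperative pain score and the regression adjusts for site only, so precision on the continuous VAS may be lost in a trial that deliberately includes chronic-pain patients

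*Combined protocol and SAP*

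**What the plan says.** - **Population.** Section X states that "patients with chronic pain syndromes will not be excluded so as to evaluate the efficacy of SHPB in this population". It also admits patients having concomitant procedures.
- **Baseline data.** The list in section XVIII opens "Detailed patient and procedure characteristics including age, race, body mass index, parity" and continues with surgical history, the indication, the type of procedure and the approach. Neither a preoperative pain score nor chronic-pain status is named.
- **Pain scores.** All those described are postoperative. In the recovery unit: "Postoperative pain scores will be collected by a registered nurse upon admission to the recovery unit, and at every hour for four hours". At home: "Patients will also be asked to complete a daily diary for one week following the procedure, which details their pain level and daily opioid consumption".
- **Primary outcome.** Section XII: "The primary outcome will be immediate postoperative patient pain scores (within 4 hours) using the Visual Analog Scale (VAS) in the recovery unit".
- **Analysis.** Section XX treats the VAS as both continuous and dichotomized. It plans t-tests, Wilcoxon tests or chi-square tests, plus a linear regression adjusting for site. Because patients are randomized, "no additional adjustment for potential confounding variables is anticipated to be necessary".
- **Response to heterogeneity.** Section XIV derives 58 patients and then says: "Accounting for heterogeneity in the patient population we aim to recruit 100 patients". Sections XII and XX add a subgroup analysis of patients operated on for pelvic pain.
- **Randomization.** Section XVI stratifies by three sites and by nothing else.

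**The concern.** Keeping chronic-pain and pain-free patients in one trial makes wide variation in preoperative pain likely. If that pain predicts recovery-unit VAS, leaving it out of the model puts its contribution into the residual variance and widens the confidence interval for the treatment difference. The reason section XX gives for not adjusting concerns confounding. It is right on that question but does not address precision.

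The plan meets heterogeneity with 42 more patients (100 - 58). It does not describe measuring one plausible source of it that a single question would capture. A preoperative score that was not recorded before surgery cannot be reliably recovered later.

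Surgery indication is collected and identifies the pelvic-pain patients, but it is used only to define a subgroup. It is a category rather than a pain intensity, and it does not cover chronic pain outside the pelvis, so it is at best a partial proxy.

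**Working it through.** **1. Reproduce the plan's figure.** Inputs from section XIV: 63% and 25%, alpha 0.05 (two-sided assumed, since sidedness is not stated), beta 0.2, 10% loss. The pooled proportion is (0.63 + 0.25)/2 = 0.44.

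n per arm = [1.960 × √(2 × 0.44 × 0.56) + 0.842 × √(0.63 × 0.37 + 0.25 × 0.75)]² / 0.38² = 25.6, rounded up to 26. The total is 52, and 52/0.9 = 57.8, rounded up to 58. The stated 58 is reproduced. It involves no baseline covariate.

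**2. Power of the design case at the planned size.** The same method gives about 98% power for 63% versus 25% with 50 per arm, and about 96% with 45 per arm after 10% loss.

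**3. Effect of adjusting the continuous VAS.** In a linear model, adding a covariate with within-arm correlation r to the outcome multiplies the variance of the treatment difference by 1 - r². Interval width is multiplied by √(1 - r²). The equivalent unadjusted sample size is 100/(1 - r²). The protocol gives no r, so a range is assumed.

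Power is for a two-sided t-test at 0.05 with 50 per arm and a difference of 0.5 SD, with the SD multiplied by √(1 - r²). The 0.5 SD is illustrative and is not in the protocol. The last column is (1.960 + 0.842) × √(2/50) × √(1 - r²), a normal approximation.

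| Assumed r | Variance removed | Interval narrower by | Equivalent N | Power at 0.5 SD | Difference detectable with 80% power |
|---|---|---|---|---|---|
| 0 | 0% | 0% | 100 | 69.7% | 0.56 SD |
| 0.1 | 1% | 0.5% | 101 | 70.1% | 0.56 SD |
| 0.2 | 4% | 2% | 104 | 71.4% | 0.55 SD |
| 0.3 | 9% | 5% | 110 | 73.7% | 0.53 SD |
| 0.4 | 16% | 8% | 119 | 77.1% | 0.51 SD |
| 0.5 | 25% | 13% | 133 | 81.6% | 0.49 SD |

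With 45 per arm, power at 0.5 SD is 65.0% unadjusted and 77.3% at r = 0.5.

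**4. Could surgery indication do the same job?** Suppose a share q of patients have a pelvic-pain indication and their mean VAS is D within-group SDs higher. The variance explained is q(1 - q)D² / [1 + q(1 - q)D²]. With D = 0.5 this is 0.04/1.04 = 3.8% at q = 0.2, and 0.0625/1.0625 = 5.9% at q = 0.5. Both q and D are assumed. A larger D of 1 would give 13.8% and 20.0%, so the proxy is weak unless the groups differ markedly.

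**The case against.** **The trial is not short of power on its own assumption.** This stands. At 63% versus 25% power is about 98%. On an assumed normal scale that effect is about 1.0 SD, where t-test power is 99.9% with or without the covariate. A reader might take the 70% figure to mean that the trial is underpowered; the protocol does not support that, because the 0.5 SD is an illustration. However, the design effect comes from abdominal hysterectomy with ropivacaine, and section XX also analyses the VAS as continuous, for which no sample size is given.

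**The correlation could be low.** This also stands. Section XI gives all patients a standard analgesic premedication and incisional anesthetic, with narcotics as needed in recovery, so high scores are treated during the outcome window. A single rating may miss intermittent pain. At r of 0.1 to 0.2 the gain is 1 to 4 patients.

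**Randomization already protects the comparison.** Correct. A reader might infer bias or an inflated type I error; neither follows. Chance imbalance in baseline pain is already allowed for in the unadjusted test and is not a second fault on top of the wider interval.

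**A form may record the score.** The baseline list is open-ended and the worksheets are not reproduced, so this cannot be ruled out. Even so, section XX specifies no use of such a score.

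**Heterogeneity has other sources.** Also fair. One might call preoperative pain the main source, but section XIV does not define heterogeneity, and concomitant procedures (section X) and operator technique (section XI) contribute too. No section ranks them.

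**The 1 - r² gain fits only one of the planned analyses.** True. It applies to the linear regression, not to the Wilcoxon or chi-square tests, and section XX does not designate the regression as primary.

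**Conclusion.** The point holds as a low-cost gain in precision, not as a flaw in validity. No section describes a preoperative pain score, site is the only covariate named, and the stated reason for adjusting no further concerns confounding rather than precision.

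For an assumed r of 0.1 to 0.5, the loss is 1% to 25% of residual variance, or about 1 to 33 patients at N = 100. Power at an illustrative 0.5 SD goes from 70% to between 70% and 82%. The benefit is a narrower interval for the continuous VAS difference and better power for effects smaller than the design effect. It is negligible if r is near zero, and these figures do not carry over to the dichotomized analysis on which the sample size rests.

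**What to change.** 1. In section XVIII, add one 0-10 pain question on the day of surgery, after consent and before randomization, asked at a consistent time relative to premedication.
2. In section XX, prespecify that score and site as covariates in the linear regression of continuous VAS, and designate that regression as the primary continuous analysis.
3. Enter site as the three-level factor used for stratification. Section XX refers to two participating sites, whereas sections IX, XIV and XVI give three; reconcile these in the same edit.
4. The sentence on confounding in section XX may stay, with a note that the pain covariate is included for precision.

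The cost is one question per patient at a visit that already takes place, and one degree of freedom. If r proves to be near zero, little is gained and almost nothing is lost.

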In an effort to reduce external factors that may influence postoperative pain, patients will be standardized to similar preoperative and postoperative medications. The standard preoperative medication regimen will include Celecoxib 200 mg po, Tylenol 975 mg po and Gabapentin 900 mg po. Patients will also receive the standard incisional anesthetic with 20 mL of 0.25% bupivacaine hydrochloride (2.5 mg/mL = 50 mg, combined with block totals 75 mg, max dose 2mg/kg therefore safe in all patients with weight over 37.5 kg). Patients will receive intraoperative narcotics at the discretion of the anesthesia team. Intraoperative narcotic use will be collected from the medical record.

The standard postoperative medication will include Toradol 30 mg IV unless a patient is 65 years of age or older or has renal or vascular disease. All patients will also receive a prescription for 20 tablets of Oxycodone 5 mg po (or 20 tablets of Hydrocodone 5 mg po or 20 tablets of Hydromorphone 2 mg po, in the event of an allergy/intolerance to Oxycodone). Note will be made of any refills during the eight-week recovery period. Patients will be provided postoperative narcotics in the recovery unit as needed per anesthesia and nursing assessment. If a patient has an allergy to any of the pre or postoperative medications, they will not receive that medication.

The block will contain 10 mL 0.25% bupivacaine hydrochloride. Bupivacaine hydrochloride is a long-acting anesthetic that is FDA-approved for local anesthesia (subcutaneous) and is routinely used at the time of laparoscopic surgery (see attached FDA approval letter and labeling). Adverse effects of bupivacaine are rare and often dose-related. Adverse effects include nausea/vomiting, anxiety, dizziness, blurred vision, and tinnitus. Toxicity can result in bradycardia, hypotension, arrhythmia, hypoventilation, apnea, and cardiac arrest. The presacral block will contain 25 mg of bupivacaine (10 mL of 0.25% bupivacaine, 2.5 mg/mL)

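### The one-week diary is the only stated source of daily home pain and opioid use, but nothing is collected or checked near day 7, so a lost or blank diary usually surfaces only around week four

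*Combined protocol and SAP*

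**What the plan says.** The combined protocol and SAP lists among its secondary outcomes (XII. Outcomes) opioid consumption and "VAS pain scores from the Brief Pain Inventory (BPI) as recorded in a patient diary for one week following surgery". XVIII. Data collection methods describes the instrument: "Patients will also be asked to complete a daily diary for one week following the procedure, which details their pain level and daily opioid consumption". On its return, the same section says that "the patient will be asked to return their postoperative diary at their routine postoperative visit (approximately four weeks after surgery".

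Four safeguards are stated:
- **Reminder (XVIII):** "patients will be contacted one to three days after surgery or discharge to remind them to complete the daily diary for one week postoperatively".
- **Chase (XVIII):** patients who book no routine visit, or who come without the diary, "will be contacted by phone or mail and a stamped and addressed envelope sent to their home address for them to return the diary".
- **Inpatient record (XVIII):** for a prolonged stay or a readmission in the first week, opioid use is taken from the medical record.
- **Supply (XI. Interventions):** "All patients will also receive a prescription for 20 tablets of Oxycodone 5 mg po", with alternatives for intolerance, and "Note will be made of any refills during the eight-week recovery period".

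XIX. Data management assigns everything not in the diary to operative and nursing forms or to the medical record. XVIII also says that most patients go home on the day of surgery.

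**The concern.** The diary is finished at the end of week one but normally stays with the patient until about week four. The chase can bring back a diary that was completed and not handed in. It cannot restore one that was lost or never filled in. By the time staff learn of such a case, daily pain scores and tablet use can only be recalled or left missing.

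At stake are the precision of the one-week pain comparison and of the home part of opioid consumption. If return depends on how well the patient recovered, the comparison may also be biased. Opioid consumption appears in the trial's hypothesis (VII. Objectives) and in the tested null hypothesis (XX. Statistical methods), so it is not a marginal endpoint. XX does not say how absent diaries will be handled.

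**Working it through.** **1. Timing.** The last diary day is about day 7 and the return visit about day 28 (XVIII). The gap is 28 - 7 = 21 days, and longer for a diary then chased by mail. For a same-day discharge, the reminder on day 1 to 3 leaves 7 - 3 = 4 to 7 - 1 = 6 diary days still to come. It is described as a reminder only, with no data capture.

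**2. Which safeguard covers which failure**

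| Failure | Reminder | Chase | Inpatient record | Refill note |
|---|---|---|---|---|
| Diary completed, not returned | no | yes | no | no |
| Diary lost | no | no | opioids only, inpatient days | supply only |
| Diary left blank | may prevent | no | opioids only, inpatient days | supply only |

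The bottom two rows are the gap.

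**3. What the supply data show.** With 20 tablets prescribed and no refill, use could be anything from 0 to 20 tablets, or 0 to 20 × 5 mg = 100 mg of oxycodone. Patients who took 2 and 18 tablets look the same. Supply bounds consumption but does not measure it. A day-7 count would: use = 20 + refill tablets dispensed by day 7 - tablets left on day 7, computed by drug. A patient with no refill and 12 tablets left (an invented example) used 20 + 0 - 12 = 8.

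**4. The plan's own loss figure.** XIV. Sample size gives 58 patients for 63% versus 25%, with alpha 0.05, beta 0.2 and 10% loss. Take a two-sided test with pooled variance and no continuity correction, with mean proportion 0.44:

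n per arm = [1.96 × √(2 × 0.44 × 0.56) + 0.842 × √(0.63 × 0.37 + 0.25 × 0.75)]² / 0.38² ≈ 25.6, so 26 per arm and 52 in total. Then 52 / 0.9 = 57.8, or 58.

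The figure reproduces. It concerns the recovery-unit VAS outcome, so its 10% is not a planned diary-return rate.

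**5. Illustrative loss of precision.** No return rate or standard deviation is given for any diary outcome, so the return rates below are assumptions, with 90% used only as a reference point. Relative interval width is √(0.9 / return). The detectable difference at 80% power, two-sided 0.05, is (1.96 + 0.842) × √(2 / m) in SD units, where m is the number of diaries per arm out of 50. Power is for an assumed 0.5 SD effect.

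| Return | m | Relative width | Detectable difference (SD) | Power at 0.5 SD |
|---|---|---|---|---|
| 90% | 45 | 1.00 | 0.59 | 66% |
| 80% | 40 | √(0.9/0.8) = 1.06 | 0.63 | 61% |
| 70% | 35 | √(0.9/0.7) = 1.13 | 0.67 | 55% |
| 60% | 30 | √(0.9/0.6) = 1.22 | 0.72 | 49% |

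**The case against.** Handing in a paper diary at a routine visit, with a reminder and a chase, is a defensible pragmatic choice that spares patients a mailing step. A diary kept daily and returned at week four loses nothing. Patients who book no visit can be spotted before week four. The rate of lost or blank diaries is unknown, and nothing in the documents shows that mailing on day 8 would raise return. All of this stands. It limits the point to lost or blank diaries and makes week four the usual, not the invariable, time of discovery.

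A reader might go further and infer that home opioid use has no check at all. The documents do not support that: the fixed prescription and the refill note give a coarse check on supply. A reader might also take late receipt as proof of late completion. A receipt date cannot show that, and a diary mailed on day 8 could have been written in one sitting.

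The tablet count has limits too. It is self-reported, it says nothing about pain, and it misses opioids from other supplies. The last matters because X. Eligibility criteria deliberately admits patients with chronic pain syndromes. A count first obtained in a later call covers that longer period, not week one.

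The diary form is an appendix that is not in the supplied text, so it may already hold some of these items.

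**Conclusion.** The point holds as a cheap, worthwhile improvement in data collection for secondary outcomes. For patients at home, daily pain and daily opioid use rest on one document that normally comes in about 21 days after its last entry. No stated step checks it near day 7 or counts tablets taken.

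The size of the loss is not known. The 6% to 22% wider intervals are an illustration that rests on assumed return of 80% to 60% against an assumed 90%. It would be tempting to present this as exceeding a planned 10% diary loss, but that allowance belongs to the recovery-unit calculation. Nor does the point reach the primary outcome or the intraoperative and recovery-unit opioid data, which nurses or the medical record supply.

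**What to change.** 1. **Return.** Give every patient the stamped envelope at discharge and ask for the diary to be mailed on day 8. Phone those whose diary has not arrived within a few days. Keep the four-week visit and the existing chase as fallback.
2. **Tablet count.** Unless the diary form already has it, add a day-7 line: was the prescription filled, which drug, how many tablets are left. Use the formula in the working, by drug and with refills limited to those dispensed by day 7, as a patient-reported cross-check and as a back-up weekly opioid total when daily entries are missing. Label any count first obtained after day 7 as covering the longer period. State that the count does not recover pain scores or opioids from other supplies.
3. **Receipt date.** Log it for description only. Treat any analysis that leaves out late diaries as a supplementary sensitivity analysis, because it may drop valid diaries from patients who merely forgot to bring them.

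The cost is up to 100 envelopes, one diary line, a mailing step for patients and a few calls. No visit is added and no treatment changes.
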